11.2.2 Observation, recording and handling of adverse events

If the researchers found that the patient had adverse events caused by acupuncture/The reaction should be recorded in CRF Centre "Bad Events /Reaction record form" And for adverse events caused by acupuncture./Responding patients give enough comfort and treatment to make them have adverse events./The reaction should be eliminated as soon as possible. If there is a serious adverse event/In addition to the above treatment, the reaction should also be immediately reported to the Second Affiliated Hospital of Guangzhou University of Traditional Chinese Medicine. There are adverse events in patients./Whether to continue the research after the reaction, first The patient's own will should be respected first, and the researchers who report adverse reactions should judge according to their professional knowledge.

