6.3 Blind law

The study includes the blind design of patients and evaluators. Only acupuncture operators know. Intervention to be used. The treatment was carried out according to the individual's schedule, so no patient had any contact with other patients in the study. In addition, all patients agree not to contact other participants and avoid talking about their treatment.

7. Interventions

This study is divided into 2 The group is the electric needle group and the false needle group respectively. The place of acupuncture treatment is Department of Neurology, Dade Road Hospital, Guangdong Provincial Hospital of Traditional Chinese Medicine. Every week 2 Times, every time 30 Minutes of electric needles (true or false), continuous 1 Months in total 8 Times (the course of treatment is 30 Oh, my God).

1· Basic treatment and emergency plan

Before starting the designated treatment plan, the patient Accepted NMOSD Guidelines for the remission period (hormonal combined immunosuppressants (immunosuppressants include thiopurine, medicophenol ester or rithitoximab)) and/Accepted NMOSD Guidelines for patients with pain (pribalin, barclofen or

gabapentine), basic treatment during the study and guidelines for patients before grouping. In the next stage of the study, all patients will start their designated treatment plan. (Electric needle) This point in time is set to 1 Day, the treatment period is 30 Oh, my God. Patients record the daily intake and intensity of analgesic drugs required. (NRS) Standardized patient diary of pain parts.

2· Test group: electric needle group

Take acupuncture points: three miles of both feet (ST36), Sanyin sex (SP6), Hegu (LI4) and Quchi (LI11), insert the needle, insert the ninth needle into the seal hall (EX-HN3)

Acupoint location reference 2006 National standards of the People's Republic of China (GB/T12346-2006 Name and Positioning of Acupoints.

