Operation process: The patient's position is supine. For acupuncturists 75% After disinfecting the acupoints on both sides of your hands and the subject, the double-sided acupuncture points will be covered with foam pads (1*1*1cm³). Acupuncture point adoption 0.25 × 0.25mm The disposable sterile acupuncture needle passes through the hollow tube and punctures into the acupuncture point through the foam adhesive pad. Acupoints, insertion angle and insertion depth are based on the references in the classic literature of traditional Chinese medicine. After taking the needle, the subjects will feel sour, numb and swollen in the local place. Connect the two electrodes of the electroneedle to the needle handle of the same limb acupuncture point., There is no positive or negative difference., Note that the metal surfaces of the two electrodes cannot be leaning against each other. Needle parameters: select sparse waves, The frequency is set to 4Hz The stimulation intensity is based on the patient's tolerance, and the needle retention time is 30 Minutes.

Control group: false needle group

Acupuncture points: acupoints used in the electric needle group Horizontal side 1cm Pay attention to avoiding traditional Chinese medicine. 14 Any corresponding area in the meridian.

Acupoint location reference 2006 National standards of the People's Republic of China (Generation B/T12346-2006 Name and Positioning of Acupoints.

Operation process: The patient's position is supine. For acupuncturists 75% After disinfecting the acupoints on both sides of your hands and the subject, the double-sided acupuncture points will be covered with foam pads (1*1*1cm³). All acupuncture points are used. 0.25 × 0.25mm The disposable sterile acupuncture needle passes through the hollow tube and punctures into the acupuncture point through the foam adhesive pad. The insertion of the needle is shallower (less than 0.2cm), it has a similar pain when a normal needle pricks into the needle. Connect the two electrodes of the electroneedle to the needle handle of the same limb acupuncture point., There is no positive or negative difference., Note that the metal surfaces of the two electrodes cannot be leaning against each

other. Needle parameters: select sparse waves, The frequency is set to 4Hz, the stimulation intensity is 0mA, the retention time is 30 Minutes.

8. Research steps

1. Screening period:

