(1) The doctor will ask, record the medical history and the results of previous examinations, conduct a comprehensive physical examination of you, and the nurse will collect the patient. 3ml Blood routine, biochemical, liver function, IL6, TNF- α Examine and take blood samples, tongue coating samples and feces samples, and collect demographic information of subjects through the inpatient medical record system.

(2) Perfect EDSS, NRS Scales, MPQ Pain scale, SDS Depression Scale, SAS Anxiety Scale, SF-36 Quality of life scale.

(3) Perfect and collect head, neck and chest MR Scan and enhance relevant data to improve fMRI Check and collect relevant data.

2. Treatment period:

The electroacupuncture group will be treated with electroacupuncture on the basis of immunotherapy and basic analgesia, and the control group will receive false acupuncture treatment on the basis of immunotherapy and basic analgesia. Every week 2 Times, every time 30 Minutes of electric needles (true or false), continuous 1 Months in total 8 Times (the course of treatment is 30 Oh, my God). Patients fill in a pain diary every day, and the treatment is carried out by the same acupuncturist. The manufacturer and use of acupuncture acupuncture needles, fake acupuncture and electroacupuncture instruments are consistent.

3. Eighth post-treatment visit (group No. 28 ± 3 Day):

(1) Patients collected by nurses 3ml The blood is routinely tested for blood, biochemical and liver function, and blood samples, tongue coating samples and feces samples are retained.

(2) Perfect EDSS, NRS Scales, MPQ Pain scale, SDS Depression Table, SAS Anxiety Scale, SF-36 Quality of life scale.

(3) Perfect fMRI Check and collect relevant data.

In this study, blood samples, tongue coating specimens and fecal samples were used to explore. NMOSD The relevant mechanism of pain in patients and the mechanism of electroacupuncture in the treatment of pain in patients with optic neuromyelitis spectrum diseases, all samples will be frozen in the Biological Resources Center of Guangdong Provincial Hospital of Traditional Chinese Medicine and preserved. 3 The sample was destroyed after the study. All samples are only used for this study, and your relevant personal information will not be made public. Researchers, personnel of the Bioresource Center and the Ethics Committee will be allowed to have access to these samples, and

subjects can request withdrawal from the reservation or research of the sample at any time.

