[figure not shown]
9. Outcome evaluation indicators

Main evaluation indicators: NRS

Pain sheet rating

Secondary evaluation indicators: EDSS、MPQ Rating, SAS Anxiety Scale, SDS Depression Scale, SF-36 Quality of life scale, IL6、TNF- α 、fMRI Indicators.

10. Technology roadmap

11.2.1 Common adverse acupuncture events/Reaction and treatment: Acupuncture has adverse reactions such as hematoma, stagnation needle, halo needle, etc.

1) Spend money/Hematoma: During acupuncture and acupuncture, local bleeding caused by puncture of blood vessels./Hematoma. Mild bleeding/Of Patients with hematoma can use disinfectant cotton swabs or cotton balls for local compression to stop the bleeding without special treatment. Moderate and severe bleeding/Patients with hematoma should be based on their bleeding./Take corresponding measures to the degree of hematoma, first stop the bleeding to prevent the increase of local swelling, carry out local anti-inflammatory treatment, and ask a surgeon to assist in dealing with it.

2) Stagnation needle: When acupuncture the stagnation needle, you should first relax the local tense muscles, and gently take the needle. Do not pull it hard. It can be opened next to the stagnant needle. 2 Enter the needle inch by inch, and then take out the stranded acupuncture needle. Severe needle stagnation should be assisted by a surgeon.

3) Needle halo: When the patient pricks the needle with acupuncture, he should quickly take out the needle and let the patient lie flat, lower his head, cushion his footsteps, and moxibustion his Baihui acupuncture point. After the patient's halo needle situation is slightly relieved, he can be ordered to drink a little warm boiled water. If the patient's needle is serious and he or she can't wake up, it should be treated according to syncope.

4) Infection: When there is redness, swelling and heat pain in the acupuncture area, the patient's affected part is told to rest and move less to reduce the spread of pain and inflammation, raise the limbs, promote reflux, reduce swelling, do not squeeze the affected part, and carry out local anti-inflammatory treatment. If necessary, you should ask a surgeon to assist in dealing with it.

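### The only instruction for entering an event on the adverse-event form (11.2.2) covers events found to be caused by acupuncture, so non-serious clinical events put down to another cause have no visible route to the form

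*Protocol*

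**What the plan says.** Section 11.2.2 covers the observation, recording and handling of adverse events. Its instruction for the CRF adverse event/reaction form reads: "If the researchers found that the patient had adverse events caused by acupuncture/The reaction should be recorded in CRF Centre". The clause on handling carries the same condition: "And for adverse events caused by acupuncture./Responding patients give enough comfort and treatment".

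Section 11.2.1, just before it, is confined to needling: "Acupuncture has adverse reactions such as hematoma, stagnation needle, halo needle, etc". It goes on to describe four event types: bleeding or hematoma, stuck needle, needle fainting, and infection of the needled area. The programme summary (section 1) gives the safety indicators as adverse reactions and three groups of laboratory tests: blood count, biochemistry and liver function.

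Serious events follow a separate route. Section 11.3.1 defines them by outcome, without reference to cause. Section 11.3.2 is headed for serious adverse events but words its trigger as a serious adverse reaction.

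On blinding, section 6.3 states: "The study includes the blind design of patients and evaluators. Only acupuncture operators know".

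**The concern.** Recording an event and deciding what caused it are two separate steps, and 11.2.2 as worded puts the second before the first. An event judged unrelated to needling need not be written down on the form, so nobody can later revisit that judgement.

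Attribution to something else is a realistic outcome in this trial, because both arms continue immunotherapy and basic analgesia throughout (sections 7 and 8). A new symptom, a side effect of a background drug, or a mild relapse that meets none of the seriousness criteria could each be put down to the disease or its treatment.

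What is at stake is the all-cause comparison of clinical adverse events between electroacupuncture and sham. That is the comparison randomisation protects, because it needs no judgement about cause. No statistical analysis plan can restore it if the events were never entered.

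**Working it through.** There is no stated figure to reproduce and no formula applies. The check is whether any visible instruction would enter, as an adverse event, a non-serious clinical event attributed to another cause. The sources of safety information are:

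- **Adverse event/reaction form (11.2.2).** Entry is instructed when the researchers find that acupuncture was the cause. The condition is not met, so nothing directs entry.
- **Laboratory tests (section 8).** Blood count, biochemistry and liver function are taken at 2 time points, screening and day 28±3, in all patients whatever the cause. They would show a laboratory abnormality, but not a clinical event as such.
- **Scales (section 8).** EDSS and the pain, mood and quality-of-life scales are scored at the same 2 time points. They yield scores and not event records.
- **Patient diary (sections 7 and 8).** It is kept daily, and the content described is analgesic use and pain. No field for other events is described.
- **Serious events (11.2.2, 11.3.1, 11.3.2).** These are captured by outcome. The definition is fairly broad, since it includes an effect on ability to work, so some relapses or drug effects would qualify. Events below that threshold do not.

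The gap is therefore limited to clinical, non-serious events attributed to something other than needling. Between the two laboratory time points lie 8 treatment sessions at which such an event has no visible instruction for entry. The 4 event types, 2 laboratory time points and 8 sessions describe the scope of the rule. They do not measure events lost.

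The text jumps from section 10 to 11.2.1, so heading 11, section 11.1 and any lead-in to 11.2 cannot be read. If a general rule stands there, two statements on recording exist side by side and 11.2.2 is the narrower. It would still need reconciling.

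**The case against.** The strongest reply is that 11.2.2 says what must be recorded and does not say that other events must not be. The form's title covers events and reactions generally, the form itself is not shown, and a general rule may stand in the unseen text. Section 11.2.2 also drops the causal qualifier later, where it turns to serious events and to whether a patient continues. In a rough translation, one phrase is thin ground for a strict reading. All of this stands as a limit: the finding is that no visible instruction enters such events, not that they are excluded. It does not remove the point, because the one recording instruction is explicit, the condition recurs in the handling clause, and the summary's safety indicators point the same way.

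Three stronger readings are tempting but not supported:

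- A reader might infer that recording will differ by arm, because the operator knows the allocation and the sham is visibly different ("The insertion of the needle is shallower (less than 0.2cm"; "the stimulation intensity is 0mA"). Nothing assigns the causality judgement to the operator, and 6.3 blinds the evaluators. The document does not show a bias by arm.
- A reader might take "the researchers who report adverse reactions should judge according to their professional knowledge" as naming who decides cause. In context it concerns whether a patient continues in the study after an event, so it says nothing on attribution.
- A reader might conclude that the whole safety comparison depends on needling-attributed events. It does not: laboratory results and serious events come in whatever the cause.

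The word reaction in 11.3.2 is also weak evidence of a causal limit on serious-event reporting. The heading and the form in that section both refer to events, and 11.2.2 asks for immediate reporting of serious adverse events.

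**Conclusion.** The point holds in a limited form. Following 11.2.2 as written gives a record of non-serious clinical events that has been filtered by cause before entry. The filtering cannot be audited afterwards, and an all-cause comparison of such events by arm is not assured.

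The size in events cannot be stated, because the protocol gives no adverse-event rate and none is assumed here. In an exploratory trial of 20 patients the safety comparison is descriptive in any case, but it should describe everything that happened. The matter belongs to the protocol and CRF, since it concerns which data are collected.

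The conclusion rests on two assumptions: that the unseen text before 11.2.1 does not already override 11.2.2, and that staff follow the instruction as worded. The correction is worth making because it is cheap and the loss would be irreversible. Confidence is medium because of the missing text. The 11.3.2 term is a minor wording matter.

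**What to change.** Reword 11.2.2 so that every adverse event from the first session to the day 28±3 visit is recorded on the CRF form in both arms, whatever its suspected cause. Make relatedness to acupuncture a separate CRF item, if the form does not already have one, judged where feasible by the evaluators who are already blinded under 6.3. Report all-cause events by arm, with acupuncture-attributed events as a subset, and bring the summary's safety indicators into line. If the text before 11.2.1 already requires all-cause recording, reconcile 11.2.2 with it. Separately, align the term in 11.3.2 with the cause-independent definition in 11.3.1.

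The cost is a few changes of wording, possibly one CRF item, the added task of judging relatedness for the evaluators, and slightly more data entry for 20 patients. Treatment, visits and sample size are unaffected.

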11.3 Serious adverse events

11.3.1 Definition: Events that require hospitalization, prolonged hospitalization, disability, affecting working ability, endanger life or death, and leading to congenital malformations occur during clinical trials.

11.3.2 Report of serious adverse events

When there is a serious adverse reaction, it should be reported to Guangzhou University of Traditional Chinese Medicine within 24 hours of the second affiliated hospital and fill in the form of serious adverse events.

12. Data management and statistical analysis

Measurement data use: average \pm Standard deviation, median (M), maximum value, Minimum value, matching is used for comparison in the counting data group. T Test (Or pairing symbol rank sum test), variance analysis is used for inter-group comparison (non-normal distribution and variance irregularity are tested by rank sum (Kruskal-Wallis)) and two comparison and calculation 95% CI. The quantitative main outcome indicators of multiple observation time points are analyzed by repeated measurement. Rank sum test is used for comparison between hierarchical data groups (Kruskal-Wallis). The counting data is expressed by composition ratio and rate, and the comparison of total efficiency groups is expressed by cal-square test (or Fisher Accurate probability method). Intergroup composition Compared with comparison 2 \times C Table or 3 \times C Table cal-square inspection.

13. Confidentiality

The results of the research through this project may be published in medical journals, but we will keep the patient's information confidential in accordance with the requirements of the law. Unless required by relevant laws, the patient's personal information will not be disclosed. If necessary, government administrations and hospital ethics committees and their relevant personnel can consult patients' information as required.

14. Ethical standards

The program of this experiment, Case report form, The informed consent form should be approved in writing by the Ethics Committee of Guangdong Provincial Hospital of Traditional Chinese Medicine before it can be carried out.

The researcher or person authorized by the researcher will be responsible for explaining the benefits and risks of participating in the trial to each patient, the legal representative of the patient or notary witness, and shall obtain the patient's written informed consent during the screening examination.

All original informed consent co-signed and signed by the subjects or their legal representatives and the person presiding over the PIC process shall be kept by the researcher.

15. Study schedules

Starting and ending date	Main research content	Expected results
--------------------------	-----------------------	------------------

2021Year11Moon-- 2022Year01Moon
	
Consult domestic and foreign literature, sort out relevant data on electroacupuncture for pain treatment, establish diagnostic criteria, inclusion, exclusion and fall off of the topic, and make observation scales.
	
Carry out a literature review, establish a medical record report form and an opening report. Unify the clinical trial method and filling in the medical record report form.

2022Year02Moon-- 2022Year12Moon
	
Apply for ethical approval and register for clinical research, conduct clinical research, establish a database, manage various materials, and enter data.
	
Complete the clinical trial registration. Complete the medical record report form. Scientifically analyze the data and write statistical reports.

	
Clinical summary, statistical analysis.
	

2022Year12Moon-- 2023Year01Moon
	
Write a closing report and a paper.
	
Apply to close the topic and publish a paper.

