6.1 Estimate of sample size

The spectrum disease of optic neuromyelitis is a rare disease, and this study is an exploratory study. Referring to previous studies, the sample size of this topic is 20 Example.

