6.2 Random grouping method

Use a simple randomization method to input the estimated sample content. SPSS V.25.0 Statistical software to obtain order numbers, random seed numbers and grouping results. Then make a random card and seal it in an opaque envelope. Before preparing to start the clinical trial, the serial number will be used according to the order in which the subjects were included in the study, the order number on the corresponding envelope will be opened, and then grouped according to the prompts on the random card. The whole process ensures randomness and secrecy and reduces the bias of researchers.

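### Section 12 treats Kruskal-Wallis as the remedy for unequal variances; with 20 patients, the resulting rule can drift from 5% when both arm size and spread differ

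*Protocol*

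**What the plan says.** Section 12 sets the between-group rule for quantitative data: "variance analysis is used for inter-group comparison (non-normal distribution and variance irregularity are tested by rank sum (Kruskal-Wallis". It adds "two comparison and calculation 95% CI", without saying what the interval estimates. Three other provisions limit the reach of this rule:

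- For a main outcome measured several times: "The quantitative main outcome indicators of multiple observation time points are analyzed by repeated measurement".
- For ordinal data: "Rank sum test is used for comparison between hierarchical data groups (Kruskal-Wallis".
- Counts go to chi-square or Fisher's exact test.

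The primary outcome is in Section 9: "Main evaluation indicators: NRS". The secondary outcomes there include the scale scores, IL6 and TNF-α. Section 6.1 states that "the sample size of this topic is 20 Example" and that "this study is an exploratory study". Section 6.2 on allocation reads "Use a simple randomization method to input the estimated sample content" and gives no ratio or arm sizes. The protocol states no significance level, standard deviation or effect size, and does not name the tests that would detect non-normality or unequal variance.

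**The concern.** With two arms, Kruskal-Wallis is the rank-sum test. Its null distribution assumes that both arms have the same distribution, so unequal spread breaks its assumption just as it breaks that of ordinary ANOVA. It can reject when the means are equal, and it supplies no interval for a mean difference. If the 95% CI in Section 12 is meant for means, test and interval may disagree.

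The switch also depends on a check of the same 20 patients. Where the check misses unequal spread, ordinary ANOVA is used under the condition the rule was meant to avoid.

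At stake is how far the p-values and intervals for single-time-point quantitative outcomes can be trusted. The direction of the error depends on which arm happens to be smaller.

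**Working it through.** **Inputs from the protocol:** 20 patients, two arms, simple randomisation, and the Section 12 rule. **Assumed, because the protocol does not give them:** two-sided 5% level, Levene (and Shapiro-Wilk) pre-tests at 5%, SD ratios, arm splits and data shape. There is no stated error rate or power to reproduce first.

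**Step 1: why arm size matters for ordinary ANOVA.** Take SDs of 2 and 1. The true variance of the mean difference is V = σ₁²/n₁ + σ₂²/n₂. ANOVA uses, on average, P = [((n₁−1)σ₁² + (n₂−1)σ₂²)/18] × (1/n₁ + 1/n₂).

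| n₁:n₂ (n₁ has SD 2) | P | V | P/V |
|---|---|---|---|
| 10:10 | 2.5 × 0.2 = 0.500 | 0.4 + 0.1 = 0.500 | 1.00 |
| 7:13 | 2 × 0.2198 = 0.440 | 0.571 + 0.077 = 0.648 | 0.68 |
| 6:14 | 1.833 × 0.2381 = 0.437 | 0.667 + 0.071 = 0.738 | 0.59 |
| 13:7 | 3 × 0.2198 = 0.659 | 0.308 + 0.143 = 0.451 | 1.46 |
| 14:6 | 3.167 × 0.2381 = 0.754 | 0.286 + 0.167 = 0.452 | 1.67 |

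Equal arms protect ANOVA. At 6:14 its standard error is √0.59 = 0.77 of the true value; at 14:6 it is √1.67 = 1.29 times the true value.

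**Step 2: the rule as a whole, by simulation.** Normal data, equal means, SD ratio 2:1, Levene check and then Kruskal-Wallis or ANOVA, 40,000 trials per setting (Monte Carlo error about √(0.05 × 0.95/40,000) = 0.1 points).

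| More variable : less variable arm | Written rule | Kruskal-Wallis alone |
|---|---|---|
| 10:10 | 5.3% | 6.2% |
| 7:13 | 8.8% | 7.6% |
| 6:14 | 11.1% | 9.7% |
| 13:7 | 2.2% | 3.0% |
| 14:6 | 1.8% | 2.9% |

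Welch's test stays between 4.7% and 5.4% in all of these. Kruskal-Wallis alone drifts too, so switching to it does not repair the problem.

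Adding the normality check (6,000 trials per setting) changes little. For SD ratios 2 to 3, the rule gives 5.4-6.3% at 10:10; 7.9-9.1% or 3.2-3.5% at 8:12; and 11.0-13.1% or 1.6-1.8% at 6:14. The higher figures arise when the smaller arm is the more variable. With SD ratios of only 1.3 to 1.5, the rule still gives about 7-9% or 2.5-4% at 7:13 or 6:14.

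**Step 3: the pre-test.** At 10:10, Levene detects a 2:1 SD ratio 42% of the time and so misses it 58% of the time. ANOVA's error among the missed cases is 6.3%. At 3:1 it detects about 75%.

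**Step 4: how likely unequal arms are.** If simple randomisation means coin tosses, Binomial(20, 0.5) gives 10:10 in 17.6% of trials, 8:12 or worse in 50%, 7:13 or worse in 26% and 6:14 or worse in 12%. Averaged over all splits, the rule's error is 5.5% at SD ratio 2 and 6.3% at ratio 3.

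**Step 5: equal spread.** When the arms share one normal distribution, the rule gives 4.8-5.5%.

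**Step 6: skewed data (exponential), equal means.** At 10:10 with SD ratio 2, the rule gives 12.5% and Welch 6.7%. In the most extreme case tried (6:14, ratio 3), the rule gives about 22% and Welch 11.4%.

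**The case against.** A reader might infer that the false-positive rate of the primary comparison is simply wrong. The documents do not support that, for five reasons.

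- **NRS may not fall under this rule.** It is scored at screening and after the eighth treatment and recorded in a daily diary, so the repeated-measures sentence plausibly governs it.
- **No stated error rate is contradicted.** The protocol gives no significance level, calls the study exploratory, and does not name a mean difference as the target.
- **If treatment changes nothing, the spreads are equal.** Randomisation then gives both arms one distribution, and the rule holds about 5%. An active arm that mixes responders and non-responders has a real mean effect, so rejecting there is not a false positive.
- **A 2:1 SD ratio is an assumption, and a large one.** As an illustration with assumed figures, if half the active arm improves by 3 points and the within-arm SD is 2, the ratio is √(4 + 0.25 × 9)/2 = 1.25. Responses of 2 to 4 points with SDs of 1.5 to 2.5 give 1.08 to 1.67.
- **The large figures are tail cases.** Under coin tosses, 6:14 or worse with the smaller arm the more variable has probability 11.5%/2 = 5.8%; for 7:13 or worse it is 13.2%.

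Nor does Section 12 send everything else to ANOVA: non-normal and ordinal data go to rank tests and counts to chi-square or Fisher. ANOVA with a rank fallback is also conventional.

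All of this limits the size and reach of the point. It does not rescue the choice of Kruskal-Wallis as the answer to unequal variance, which the protocol states outright and does not leave to a later plan.

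**Conclusion.** The point holds in limited form. Section 12 prescribes a data-driven switch to a test that does not solve the problem for which it is invoked and gives no interval for a mean difference. It applies to single-time-point quantitative outcomes, including IL6, TNF-α and scale scores treated as quantitative, and to NRS only if it is compared at one time point.

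For normal data the error stays near 5% with equal spread, and at 5.3-6.3% at 10:10 with SD ratios of 2 to 3. It moves to about 8-11% or 2-3% at a 2:1 ratio when the arms are also unequal in size. These sizes rest on the assumed level, pre-tests, SD ratios and splits. In an exploratory trial of 20 patients this is a cheap improvement of minor to moderate weight.

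**What to change.** In Section 12, delete unequal variance as a reason to use Kruskal-Wallis and substitute wording such as: *Quantitative outcomes are compared between the two groups by Welch's t-test, or by a model with heteroscedasticity-robust errors (including for repeated measures), with the matching 95% CI and without a variance pre-test. The rank-sum test is a sensitivity analysis.* The provisions for ordinal and count data can stay.

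The cost is this change of wording and, if the variances are equal, about 0.5 points of power (79.7% to 79.2% at 10:10 with a standardised difference of 1.325). Welch is not exact for strongly skewed data with unequal spread (3.9% to 11.4% in the settings tried), which is why the rank-sum test should be kept as a sensitivity analysis.

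### Section 12 names no NRS analysis that adjusts for the screening NRS, although every eligible patient has one; adding it as a covariate costs almost nothing and usually gains precision

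*Protocol*

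**What the plan says.** Section 9 of the protocol makes the pain score the main outcome: "Main evaluation indicators: NRS". Section 12 then gives two statements that reach it.

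- On measurements at several time points: "The quantitative main outcome indicators of multiple observation time points are analyzed by repeated measurement".
- On comparison between groups of measurement data in general: "variance analysis is used for inter-group comparison (non-normal distribution and variance irregularity are tested by rank sum (Kruskal-Wallis".

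Only the first is tied explicitly to the main outcome. The second reaches NRS because NRS is a measurement. Neither statement, nor any other part of the protocol, mentions a covariate, a baseline adjustment or ANCOVA.

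NRS is measured as follows.

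- Section 5.1 requires a score of at least 4 for entry.
- Section 8 lists it in the screening period ("Perfect EDSS, NRS Scales, MPQ Pain scale, SDS Depression Scale") and again at the visit after the eighth treatment, day 28 ± 3 ("Perfect EDSS, NRS Scales, MPQ Pain scale, SDS Depression Table").
- Section 8 also has a daily record during treatment, "Patients fill in a pain diary every day". Section 7 indicates that this diary carries pain intensity as NRS.

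Section 6.1 sets the sample at 20, calls the study exploratory and gives no effect size, SD or power. Section 6.2 specifies simple randomisation and does not mention stratifying by baseline pain.

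**The concern.** With 20 patients in a rare disease and no power target, the useful product of the trial is an estimate of the NRS difference and its interval. A pre-treatment NRS is available for every eligible patient. Using it as a covariate removes the part of the outcome variance that it predicts, and corrects for chance imbalance that simple randomisation of 20 patients does not prevent.

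The methods named in section 12 leave this out in different ways.

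- A comparison of the final score alone does not use the screening value.
- A classical repeated-measures ANOVA on the two clinic visits uses it only as a time point. Its group-by-time test is then a comparison of change scores, which is inefficient unless baseline and final score are highly correlated.
- A repeated-measures analysis of the diary compares diary values, and its group effect does not involve the screening score.

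An analyst could follow section 12 to the letter and obtain a wider interval than the same data allow.

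**Working it through.** **Plan's own figure.** The sample size of 20 (section 6.1) cannot be reproduced, because the protocol gives no effect size, SD, alpha or power. What follows compares methods at that sample size.

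**Inputs.** From the protocol: 20 patients in two groups, NRS at screening and at day 28 ± 3, and a 95% CI (taken as two-sided alpha 0.05). Assumed, because the protocol does not give them: 10 per arm, a true difference of 1 SD, and correlation ρ between screening and final NRS of 0.3, 0.5 or 0.7.

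**Formulas.** In units of the outcome variance, the effective variance V is:

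- final score only: V = 1, 18 df;
- change score, or group-by-time in a classical two-visit ANOVA: V = 2(1 − ρ), 18 df;
- ANCOVA: V = (1 − ρ²)(1 + 1/16), 17 df, where the second factor is the cost of estimating the slope.

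The noncentrality is 1 × √(10/2)/√V = 2.236/√V, and power comes from the noncentral t distribution.

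| ρ | V final / change / ANCOVA | Noncentrality | Power |
|---|---|---|---|
| 0.3 | 1 / 1.4 / 0.967 | 2.236 / 1.890 / 2.274 | 0.56 / 0.43 / 0.57 |
| 0.5 | 1 / 1.0 / 0.797 | 2.236 / 2.236 / 2.505 | 0.56 / 0.56 / 0.66 |
| 0.7 | 1 / 0.6 / 0.542 | 2.236 / 2.887 / 3.038 | 0.56 / 0.78 / 0.82 |

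Simulation agrees with these to within about one point.

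**Gain from the covariate.** In power points it is about 1/10/26 over the final score and 14/9/4 over the change score at ρ = 0.3/0.5/0.7. Simulated mean 95% CI widths are 1.82/1.66/1.37 SD for ANCOVA against 2.19/1.85/1.44 SD for the change score, so about 17%, 10% and 5% narrower. Against final-score ANOVA, 20 patients under ANCOVA are worth 20/V, or about 21, 25 and 37 patients.

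**Entry floor.** Requiring NRS of at least 4 narrows the baseline range. I simulated integer NRS bounded at 0 to 10, with assumed population mean/SD of 5.5/1.6, 5.0/2.0 and 6.0/1.6. The correlation falls from 0.3/0.5/0.7 to about 0.22-0.26/0.38-0.44/0.57-0.63. The gain becomes about 0/4-6/14-19 points over the final score and 8-12/4-8/1-3 points over the change score.

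**Diary.** Assume the mean of seven days, a constant effect of 1 single-day SD and day-to-day correlation c. Without a covariate, V = c + (1 − c)/7, which is 0.571/0.743/0.829 at c = 0.5/0.7/0.8, and power is 0.80/0.69/0.64. With the screening NRS as covariate, V = (c + (1 − c)/7 − ρ²)(1 + 1/16), where ρ is now its correlation with a single day. At c = 0.7 power rises from 0.69 to 0.72/0.83/0.98. A group-by-day interaction test is not covered by this calculation.

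**Cost.** At ρ = 0 ANCOVA has V = 1.0625 and power 0.53, against 0.56 for the final score: about 3 points lost.

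**The case against.** *This belongs in a statistical analysis plan.* Covariates are often left there, and the phrase about repeated measurement names a family of methods without excluding a covariate. That is fair as far as it goes. But section 12 has already chosen the test families for NRS, and the point concerns that choice. A plan not shown could still add the covariate.

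*Repeated measures already uses the baseline.* This stands in part. On two visits the screening score enters as a time point, so a reader who inferred that the plan ignores it would go too far. The equivalence with a change score holds only for the classical ANOVA. A longitudinal model that constrains the baseline means to be equal across arms has about the efficiency of ANCOVA and is also a repeated-measures analysis. Section 12 does not say which is meant.

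*A single-visit ANCOVA can be the weaker analysis.* This stands. A reader might infer that the day 28 ± 3 score should become primary and repeated measures secondary. Under the diary assumptions, even the unadjusted seven-day mean (0.80/0.69/0.64) beats single-visit ANCOVA at ρ = 0.3 (0.57), and in two of three cases at ρ = 0.5 (0.66). The protocol gives no ground for that demotion.

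*The gain may be small.* At each end of the correlation range one unadjusted option nearly matches ANCOVA. But it is a different option at each end, and the protocol gives no correlation by which to choose between them.

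A reader might also infer that the switch to Kruskal-Wallis for unequal variances needs replacing. That would rest on an assumed trigger, assumed SD ratios and an assumed unequal split. Section 6.2 does not state the split, and at 10:10 the simulated switch keeps type I error at 5-6%. The documents do not support a finding there.

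**Conclusion.** The point holds as one of precision. Section 12 names no between-group NRS analysis with the screening NRS as a covariate, although that score exists for every eligible patient. The unadjusted tests remain valid under randomisation, so nothing here says that their p-values or intervals would be wrong.

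Under the assumed 10 v 10, 1 SD difference and ρ of 0.3/0.5/0.7, adjustment matches or beats both unadjusted single-visit options throughout. It is worth most where the analyst happened to pick the wrong one: the change score at low correlation, or the final score at high correlation. With the entry floor, the gain over the final score disappears at 0.3 and the gain over the change score is 1-3 points at 0.7. All sizes rest on correlations, SDs and an arm split that the protocol does not give. The change is worth making because it is cheap and because a study of 20 in a rare disease cannot easily recover precision by adding patients.

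**What to change.** In section 12, state that whichever between-group NRS analysis is primary includes the screening NRS as a covariate and reports the adjusted mean difference with its 95% CI:

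- if only the day 28 ± 3 score is compared, ANCOVA on group and screening NRS;
- if several time points are used, the repeated-measures model of post-baseline NRS, including the diary, with the screening NRS as covariate.

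Repeated measures need not be demoted, and this point does not ask for the rank-sum fallback to be replaced.

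The cost is wording in one section and one error degree of freedom, about 3 power points if screening and final NRS are uncorrelated. No new measurement or visit is needed.
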